12.2 Clinical Laboratory Tests

Hematology, blood chemistry, and urinalysis data are collected at Screening, Day 5, Day 14, and Follow-up/End of Treatment. They will be summarized by treatment group at each visit, as well as change from Baseline for continuous parameters at post-baseline visits.

- Hematology: hemoglobin, hematocrit, red blood cells (RBC), white blood cells (WBC) with differential, lymphocytes, monocytes, neutrophils, eosinophils, basophils, platelets, and their change from Baseline, will be summarized by treatment group at each visit with continuous statistics (n, mean, SD, median, minimum and maximum).
- Chemistry and Coagulation: albumin, alkaline phosphate, alanine amino transferase, aspartate amino transferase, bicarbonate, total bilirubin, direct bilirubin, blood urea nitrogen (or urea), calcium, chloride, creatinine, lactate dehydrogenase, phosphate, inorganic, potassium, total protein, sodium, partial thromboplastin time, and activated partial thromboplastin time, and their change from Baseline, will be summarized by treatment group at each visit with continuous statistics (n, mean, SD, median, minimum and maximum).
 - Glucose is only collected at Baseline, so there will not be any post-baseline or change from baseline summaries.
 - Creatine kinase-MB, creatinine kinase, and troponin are only collected in special cases; they will be listed, but not summarized.
- Urinalysis:
 - Specific gravity and pH, and their change from Baseline, will be summarized by treatment group at each visit with continuous statistics (n, mean, SD, median, minimum and maximum).
 - Categorical parameters glucose, protein, blood, ketones, bilirubin, urobilinogen, nitrite, and leukocyte esterase will be summarized with counts and percentages by treatment group at each visit.
 - Urine sedimentation count (erythrocytes [RBC], leukocytes [WBC], and epithelial cells) and urine microscopy (crystals, casts, and bacteria) will be listed.

Summaries of counts and percentages of laboratory parameters that are Low, Normal, and High compared to the reference ranges will be presented by treatment at each visit and time point. Shift tables will be presented for laboratory parameters with defined DMID grades. DMID grades are defined in Appendix 17.4, DMID Adult Toxicity Table.

All clinical laboratory results will also be listed; these listing will be sorted by subject, visit date, and lab parameter; they will also include DMID grades and the low, normal and high value flags.

Separate listings of subjects with any clinical laboratory test result outside the reference ranges will also be presented for hematology, chemistry and coagulation, and urinalysis parameters. For these listings, if a subject has a DMID grade 1 or higher value, or low and/or high flag for a parameter, or a non-normal value for a categorical urinalysis parameter, all data for that subject/parameter will be presented. These listings will be sorted by subject, parameter, then visit. An additional listing will be presented for subjects with more than a 2-grade shift in DMID grades in any lab parameter.

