Relative changes in clinical laboratory test values compared with values at baseline will be evaluated in according to the Division of Microbiology and Infectious Diseases (DMID) grading table or in accordance with the normal ranges of the clinical laboratory (below, within, or above normal range) for parameters for which no toxicity grades are defined. A shift from baseline table of abnormalities in clinical laboratory test parameters will be provided by assessment time point and by treatment group.

A listing of subjects with any clinical laboratory test result outside the reference ranges will be provided.

Vital Signs

Actual values and changes from baseline of heart rate, respiratory rate, temperature, SBP, and DBP measurements will be evaluated by means of descriptive statistics by assessment time point and by treatment group.

A shift from baseline table of vital sign abnormalities will be provided by assessment time point and by treatment group.

Electrocardiography

The ECG variables that will be analyzed are heart rate, PR interval, QRS interval, and QT interval. Values for QT corrected for heart rate (QTc) will be derived. QTc corrected according to Fridericia (QTcF) [6] will be the primary correction parameter.

Actual values and changes from baseline of ECG variables will be evaluated by means of descriptive statistics by assessment time point and by treatment group.

A shift from baseline table of ECG abnormalities will be provided by assessment time point and by treatment group. For absolute QTcF interval prolongation (>450, >480, >500 msec) and changes from baseline (increase >30 and >60 msec), a frequency table by assessment time point and by treatment group will be provided.

Physical Examination

Abnormal findings in physical examination will be listed.

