APPENDIX 1: LABORATORY ASSESSMENTS

Urinalysis	Hematology	Chemistry
Dipstick: 
 • Specific gravity • pH • Glucose • Protein • Blood • Ketones • Bilirubin • Urobilinogen • Nitrite • Leukocyte esterase Urine sedimentation count: 
 • Erythrocytes (RBC) • Leukocytes (WBC) • Epithelial cells Microscopy 
 • Crystals • Casts • Bacteria 	Hemoglobin Hematocrit Red blood cells (RBC) White blood cells (WBC) with differential Lymphocytes Monocytes Neutrophils ^c Eosinophils Basophils Platelets	Albumin Alkaline phosphate Alanine amino transferase Aspartate amino transferase Bicarbonate Total bilirubin Direct bilirubin ^b Blood urea nitrogen (or urea) Calcium Chloride Creatinine Glucose ^a Lactate dehydrogenase Phosphate, inorganic Potassium Total protein Sodium Creatine kinase-MB ^d , creatinine kinase ^d , troponin ^d
Serology ^a	Other Assessments	Coagulation
Antibody screening test (immunoassay), rapid HIV test	Urine pregnancy test	Partial thromboplastin time Activated partial thromboplastin time

a Screening only

b Assay if total bilirubin is above normal range.

c If immature neutrophils are detected, the sample is to be flagged and a blood slide for microscopic analysis will be made. If Bands are detected in the microscopic analysis, then a result will be provided.

d Only measure if subject has chest pain.

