16.4 DMID Adult Toxicity Table

ABBREVIATIONS: Abbreviations utilized in the Table:

ULN = Upper Limit of Normal

LLN = Lower Limit of Normal

R_x = Therapy

Req = Required

Mod = Moderate

IV = Intravenous

ADL = Activities of Daily Living

Dec = Decreased

HEMATOLOGY				
	Grade 1	Grade 2	Grade 3	Grade 4
Hemoglobin	9.5 - 10.5 g/dL	8.0 - 9.4gm/dL	6.5 - 7.9 g/dL	< 6.5 g/dL
Absolute Neutrophil Count	1000-1500/ mm ³	750-999/ mm ³	500-749/ mm ³	<500/ mm ³
Platelets	75,000-99,999/ mm ³	50,000-74,999/ mm ³	20,000-49,999/ mm ³	<20,000/ mm ³
WBCs	11,000-13,000/mm ³	13,000-15,000/mm ³	15,000-30,000/ mm ³	>30,000 or <1,000/mm ³
% Polymorphonuclear Leucocytes + Band Cells	> 80%	90 – 95%	>95%	-----
Abnormal Fibrinogen	Low: 100-200 mg/dL High: 400-600 mg/dL	Low: <100 mg/dL High: >600 mg/dL	Low: < 50 mg/dL -----	
Fibrin Split Product	20-40 mcg/ mL	41-50 mcg/ mL	51-60 mcg/ mL	> 60 mcg/ mL
Prothrombin Time (PT)	1.01 - 1.25 x ULN	1.26-1.5 x ULN	1.51 -3.0 x ULN	>3 x ULN
Activated Partial Thromboplastin (APPT)	1.01 -1.66 x ULN	1.67 - 2.33 x ULN	2.34 - 3 x ULN	> 3 x ULN
Methemoglobin	5.0 - 9.9 %	10.0 - 14.9 %	15.0 - 19.9%	> 20.0 %

CHEMISTRIES				
	Grade 1	Grade 2	Grade 3	Grade 4
Hyponatremia	130-135 mEq/ L	123-129 mEq/ L	116-122 mEq/ L	< 116 mEq/ L
Hypertatremia	146-150 mEq/ L	151-157 mEq/ L	158-165 mEq/ L	> 165 mEq/ L
Hypokalemia	3.0 - 3.4 mEq/ L	2.5 - 2.9 mEq/ L	2.0 - 2.4 mEq/ L or intensive replacement therapy or hospitalization required	< 2.0 mEq/ L
Hyperkalemia	5.6 - 6.0 mEq/ L	6.1 - 6.5 mEq/ L	6.6 - 7.0 mEq/L	> 7.0 mEq/ L
Hypoglycemia	55-64 mg/dL	40-54 mg/dL	30-39 mg/dL	<30 mg/dL
Hyperglycemia	116 - 160 mg/dL	161- 250 mg/dL	251 - 500 mg/dL	> 500 mg/dL
Hypocalcemia	8.4 - 7.8 mg/dL	7.7 - 7.0 mg/dL	6.9 - 6.1 mg/dL	< 6.1 mg/dL
Hypercalcemia	10.6 - 11.5 mg/dL	11.6-12.5 mg/dL	12.6 - 13.5 mg/dL	> 13.5 mg/dL
Hypomagnesemia	1.4 - 1.2 mEq/ L	1.1 - 0.9 mEq/ L	0.8 - 0.6 mEq/ L	< 0.6 mEq/ L
Hypophosphatemia	2.0 - 2.4 mg/dL	1.5 -1.9 mg/dL or replacement Rx required	1.0 -1.4 mg/dL intensive therapy or hospitalization required	< 1.0 mg/dL
Hyperbilirubinemia	1.1 - <1.25 x ULN	1.25 - <1.5 x ULN	1.5 – 1.75 x ULN	> 1.75 x ULN
Hyperbilirubinemia	1.1 - <1.5 x ULN	1.5 - <2.0 x ULN	2.0 – 3.0 x ULN	> 3.0 x ULN
BUN	1.25 - 2.5 x ULN	2.6 - 5 x ULN	5.1 - 10 x ULN	> 10 x ULN
Hyperuricemia (uric acid)	7.5 – 10.0 mg/dL	10.1 – 12.0 mg/dL	12.1 – 15.0 mg/dL	>15.0 mg/dL
Creatinine	1.1 - 1.5 x ULN	1.6 - 3.0 x ULN	3.1 - 6 x ULN	> 6 x ULN

ENZYMES				
	Grade 1	Grade 2	Grade 3	Grade 4

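### SAP 12.2 limits blood-test shift tables to DMID-graded parameters, so 13 of 28 tests lose the normal-range shift that Protocol 9.3.8 provides, and SAP 16.1 does not declare it (minor)

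*SAP*

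**What the plan says.** Protocol 9.3.8 (repeated in the synopsis) evaluates laboratory change from baseline by DMID grade and otherwise "in accordance with the normal ranges of the clinical laboratory (below, within, or above normal range) for parameters for which no toxicity grades are defined". It then commits to a display: "A shift from baseline table of abnormalities in clinical laboratory test parameters will be provided by assessment time point and by treatment group". Nothing in that sentence confines the display to graded tests.

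SAP 12.2 is narrower: "Shift tables will be presented for laboratory parameters with defined DMID grades". The table list in SAP 16.6.1 agrees for blood tests, because Tables 14.3.5.3 (hematology) and 14.3.5.6 (chemistry and coagulation) are both by DMID grade. For normal ranges the SAP keeps Low/Normal/High counts at each visit (Tables 14.3.5.2 and 14.3.5.5). It also keeps summaries of change from baseline, and listings that show all of a subject's values for any flagged parameter. Urinalysis has its own shift table that does not depend on DMID grades (14.3.5.9).

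SAP 16.1 declares changes to ADA sampling, viral-load sampling and QTcF categories. It has no laboratory item.

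Two further texts bear on the point. The top grade on the WBC row of SAP 16.4 reads ">30,000 or <1,000" per mm³, and its lowest high-side grade starts at 11,000; Protocol Appendix 2 has the same row. For direct bilirubin, the note in Protocol Appendix 1 is "Assay if total bilirubin is above normal range".

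**The concern.** Safety is the primary objective and subjects enter with acute influenza, so some blood values may be abnormal at baseline and recover during follow-up. A count of low or high values at a visit then mixes subjects who have not yet recovered with subjects who have become abnormal since dosing. A shift table separates the two groups by arm, and Protocol 9.3.8 promises one. If ungraded tests have no shift table, a reader of the summary tables cannot make that separation for them. An undeclared departure also leaves nobody able to tell whether it was intended. It looks inadvertent, since the SAP plans shift tables for vital signs (12.3), ECG (12.4) and categorical urinalysis.

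**Working it through.** **Count of tests.** The inputs are the test lists in SAP 12.2 and the grade rows in SAP 16.4. The documents give no figure of their own to reproduce. Hematology is "hemoglobin, hematocrit, red blood cells (RBC), white blood cells (WBC) with differential, lymphocytes, monocytes, neutrophils, eosinophils, basophils, platelets": 10 tests. Chemistry and coagulation is "albumin, alkaline phosphate, alanine amino transferase, aspartate amino transferase, bicarbonate, total bilirubin, direct bilirubin, blood urea nitrogen (or urea") followed by "calcium, chloride, creatinine, lactate dehydrogenase, phosphate, inorganic, potassium, total protein, sodium, partial thromboplastin time, and activated partial thromboplastin time": 8 + 10 = 18 tests. Blood glucose is left out because it is collected only at baseline, and CK-MB, creatine kinase and troponin because they are listed only. Total: 10 + 18 = 28.

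| Group | With a DMID row | Without |
|---|---|---|
| Hematology (10) | 4: hemoglobin, WBC, neutrophils, platelets | 6: hematocrit, RBC, lymphocytes, monocytes, eosinophils, basophils |
| Chemistry/coagulation (18) | 11: ALP, ALT, AST, total bilirubin, BUN, calcium, creatinine, phosphate, potassium, sodium, aPTT | 7: albumin, bicarbonate, direct bilirubin, chloride, LDH, total protein, PTT |
| All (28) | 15 | 13 |

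13/28 = 46%. If either PTT is read onto the aPTT row or direct bilirubin onto the hyperbilirubinemia rows, the share is 12/28 = 43%; with both, 11/28 = 39%.

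**What per-visit counts can hide.** Illustration with assumed rates and 150/3 = 50 subjects per arm: 20% low at baseline in both arms, half of these recovered by Day 5, and a further 10% of the arm newly low on VIS410 only.

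- VIS410: 10 low at baseline; 10 − 5 + 5 = 10 low at Day 5. The counts read 20% then 20%.
- Placebo: 10 low at baseline; 10 − 5 + 0 = 5 low at Day 5. The counts read 20% then 10%.

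The VIS410 counts would be identical if none of the 10 had recovered and nobody were newly low. With 10 low at each time, the number newly low is 10 minus the number still low, which can be anything from 0 to 10. The counts cannot say whether recovery was slower or new cases arose; the shift table would show 5 new cases against 0.

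**WBC row.** Every value from 1,000 to below 11,000/mm³ is ungraded. A fall from 7,000 to 1,500 is therefore grade 0 to 0, and a fall from 12,000 to 1,500 is grade 1 to 0, which reads as improvement. The neutrophil row covers part of this. Neutrophils cannot exceed total WBC, so at a WBC of 1,500 they are at most 1,500/mm³, which is at least Grade 1 (1,000–1,500). At higher WBC values, a fall that leaves neutrophils above 1,500 because it is driven by lymphocytes shows on neither row, and lymphocytes have no row.

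**Direct bilirubin.** A value exists only at visits where total bilirubin is above normal, so a change from baseline exists only for subjects with raised total bilirubin both before dosing and at that visit. The mean and mean change in SAP 12.2 thus describe a selected group that differs from visit to visit. SAP 12.2 lists CK-MB and troponin without summary for that kind of reason.

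**The case against.** The strongest reply is that little is lost. For any subject with an out-of-range flag, SAP 12.2 lists all results for that parameter in visit order, so baseline and later values can be linked for every ungraded test. Change from baseline is summarized for all 28 tests. This stands: what is missing is the aggregate cross-tabulation by arm, not the data. Even in the illustration the arms differ at Day 5 (20% against 10%); what is hidden is the reason.

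The clinical stakes are also modest. Sodium, potassium, BUN, creatinine, calcium and phosphate are graded and so have shift tables. Hematocrit and RBC largely track hemoglobin, which is graded. The GI events described in Protocol 1.3 mostly resolved within about 24 hours, while the first scheduled post-dose draw is Day 5, so a bicarbonate or chloride shift table would say little about them. Protocol 1.3 also reports no electrolyte alterations in subjects with loose stool or diarrhea in Study VIS410-102. The Phase 1 leukopenia event was judged unrelated and secondary to a primary HSV-1 infection, so it does not raise the stakes. The primary endpoints are proportions with adverse events, not laboratory shifts.

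A reader might infer that dropping the normal-range rule is what hides a fall in WBC. The documents do not support this. WBC is graded, so Protocol 9.3.8 also sends it to the DMID table, with the same gap. Neither document gives a WBC reference range, so the ungraded interval they support is 1,000 to below 11,000/mm³, not one that ends at a stated lower limit of normal. A reader might also infer that all laboratory shift tables are confined to DMID grades; Table 14.3.5.9 shows otherwise for urinalysis.

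**Conclusion.** The conflict between Protocol 9.3.8 and SAP 12.2 is real and undeclared. On a literal match, 13 of 28 blood tests (11 or 12 if direct bilirubin and/or PTT are mapped to existing rows) have no aggregate shift from baseline, so their summary tables cannot separate recovery from new abnormality by arm. This rests on reading the protocol's shift-table sentence together with the classification rule just before it. The WBC gap is a separate limitation of the DMID row in both documents, partly covered by the neutrophil row. The averaging of direct bilirubin is a small separate error of summary. Severity is minor: a supportive safety display is incomplete, individual data are retained, and no primary endpoint is affected.

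**What to change.** In SAP 12.2 and the table list in 16.6.1:

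- Add Low/Normal/High shift-from-baseline tables, by visit and arm, for the ungraded hematology, chemistry and coagulation tests other than direct bilirubin (12 tests on the literal match). This restores what the protocol promises.
- Add the same table for WBC. This goes beyond the protocol's wording, since restoring its rule alone would leave WBC unchanged.
- List direct bilirubin without means or changes, as is done for CK-MB and troponin, and record that choice in SAP 16.1.

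If the sponsor prefers to keep shift tables to graded tests, SAP 16.1 should at least declare and justify the change. That would close the documentation gap but not the gap in the display.

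Cost: two or three extra tables from the flags already derived for Tables 14.3.5.2 and 14.3.5.5, and no new data.

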12.3 Vital Signs

Vital signs heart rate, respiratory rate, temperature, systolic blood pressure, and diastolic blood pressures are recorded at Screening, on Day 1: Baseline, Day 1: End of Infusion Day 1: ≥ 2 hours post end of infusion, Day 3, Day 5, Day 7, Day 14, Day 28, Day 56 and Day 100/Early termination.

Tables presenting vital signs will display summary statistics (n, mean, SD, median, minimum and maximum) for the observed data at each visit. The corresponding changes from Baseline at the post-baseline visits will also be presented. Temperature will be presented in degrees Celsius.

Summaries of counts and percentages of vital signs that are Not Done, Normal, Abnormal, and Abnormal - Clinically Significant will be presented by treatment at each visit and time point. Shift tables of changes from baseline will also be presented.

Summaries of counts and percentages for subjects meeting Potentially Clinically Significant (PCS) Post-Baseline Vital Sign Criteria by visit will be presented. The PCS criteria for vital signs can be referenced in Appendix 17.5. A listing of these subjects meeting PCS criteria will also be provided.

All vital signs data will be listed. Subjects also self-monitor their temperature daily. These data will be summarized with the diary data, an efficacy endpoint; see sec. 10.1.2.

12.4 ECG Data

ECGs are performed at Screening and at Day 1: End of Infusion. The heart rate, PR interval, QRS interval, QT interval, and corrected QT, using the Fridericia correction (QTcF) will be summarized; change from Baseline at the post-infusion measurement will also be summarized. The QTcF calculation will be derived within the EDC system.

Counts and percentages of subjects with QTcF interval prolongation categories of <450 , >450 to ≤ 480 , >480 to ≤ 500 , and >500 msec, will be presented by treatment group and visit. A similar

summary will be presented for subjects with QTcF increases of <30, >30 to ≤60 and >60 msec from Baseline.

A summary of normal and abnormal results, as well as shifts from Baseline for the post-infusion ECG, will be summarized with counts and percentages by treatment group.

Any clinically significant ECG findings will be collected and summarized with AEs.

All ECG data will be listed. A listing of subjects with QTcF interval prolongation of >450 to ≤480, >480 to ≤500, and >500 msec and/or QTcF increases of >30 to ≤60 and >60 msec from Baseline will be presented.

12.5 Physical Exam

A complete physical exam is only performed at Screening. A targeted physical exam may be performed at the Investigator's discretion at any time point during the study. A summary of physical examination results at Baseline will be presented by treatment group. All physical exam data will be listed.

13 INTERIM ANALYSIS

Optional interim analyses may be performed after 75 subjects have completed the Day 28 visit and/or after all enrolled subjects have completed the Day 14 visit. If the interim analyses are performed, a list of needed TFLs will be provided to the independent unblinded biostatistics team. These TFLs may be presented as completely unblinded analyses or in a semi-unblinded fashion, i.e. using coded actual treatment groups.

A Data Safety Monitoring Board (DSMB) will be empaneled to monitor the safety of the enrolled subjects. The tasks and responsibilities of the DSMB will be documented in a separate document.

14 SOFTWARE AND PROGRAMMING SPECIFICATIONS

14.1 Statistical Software

All statistical analyses will be performed using SAS 9.4 or higher, in accordance with Pharm-Olam SOP 009-20- SAS Program Development and Change Control. Specialized PK software will be used for some PK analyses.

14.2 General Programming Specifications

All tables will include the sponsor name, protocol ID, "Page x of y" and "Draft" or "Final" in the header.

The last 2 footer lines will be:

1. Data Source: (a data set for listings, a listing reference for tables) left justified
2. "Program Location: E:\Projects\1016Visterra\Stats\Programs\xxx.sas" left justified and "Date-Time: DDMMYY:HH:MM" right justified

16 APPENDICIES

16.1 Changes to the Protocol Specified analyses

ADA data at Day 14 will not be analyzed.

Nasopharyngeal viral load samples will only be analyzed for qPCR and TCID₅₀ until Day 7, unless still positive on Day 7, and then samples will also be analyzed on Day 14. No PCR or TCID₅₀ samples are planned to be analyzed post-Day 14.

QTcF interval prolongation categories were updated to <450, >450 to ≤480, >480 to ≤500, and >500 msec and categories for QTcF increases were updated to <30, >30 to ≤60 and >60 msec from Baseline.

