¹⁷ Subjects will be observed during infusion and at least 2 hours after completing the infusion of VIS410 to allow monitoring for possible hypersensitivity reactions. VIS410 will be administered over 2 hours. Infusion time can be extended at discretion of the Investigator up to 4 hours based on local infusion-related symptoms. If any serious systemic reactions occur, the infusion of VIS410 can be slowed or stopped at the discretion of the Investigator.

¹⁸ Within 1 hour prior to VIS410 administration.

¹⁹ Sample collected within 30 minutes after completing the infusion of VIS410/placebo.

²⁰ Nasopharyngeal swabs will be obtained from both nostrils (1 swab per nostril).

²¹ Will be done for the first 50 subjects enrolled only.

²² If a subject presents with or reports influenza-like illness, additional swabs (1 swab per nostril) should be taken (see Section 7.1.5).

LIST OF ABBREVIATIONS AND DEFINITIONS OF TERMS

Abbreviation	Definition
ADA	Anti-drug antibody
AE	Adverse event
AESI	Adverse event of special interest
AUC	Area under the curve
AUC _{0-∞}	Area under the concentration-time curve extrapolated to infinity
AUC _{0-last}	Area under the concentration-time curve from time 0 to the last measurable concentration
CD-1	Cluster of differentiation 1
CL	Clearance
C _{max}	Maximum serum concentration
CRO	Contract Research Organization
DBA	Dilute Brown Non-Agouti
DBP	Diastolic blood pressure
DMID	Division of Microbiology and Infectious Diseases
DSMB	Data Safety Monitoring Board
EC ₅₀	Half-maximal effective concentration
EDC	Electronic data capture system
GCP	Good Clinical Practice
GI	gastrointestinal
GLP	Good Laboratory Practice
HA	Hemagglutinin
HAI	Hemagglutination inhibition assay
HIV	Human immunodeficiency virus
ICF	Informed Consent Form
ICH	International Conference on Harmonization
IEC	Independent Ethics Committee
IgG1	Immunoglobulin G1
IRB	Institutional Review Board
ITT	Intent-to-treat
IV	Intravenous
LSLV	Last Subject Last Visit
MedDRA	Medical Dictionary for Regulatory Activities
mITT	Modified intent-to-treat
NOAEL	No-observed-adverse-effect level
NSAID	Non-steroidal anti-inflammatory drug
PK	Pharmacokinetic
PO	Oral (by mouth)
qRT-PCR	Quantitative reverse transcriptase polymerase chain reaction
SAE	Serious adverse event
SAP	Statistical analysis plan
SBP	Systolic blood pressure
SUSAR	Suspected unexpected serious adverse reaction
t _{1/2}	Elimination half-life
TCID ₅₀	Half-maximal tissue culture infective dose

Abbreviation	Definition

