11.2 Nasopharyngeal Viral Load

Standard non-compartmental approaches using Phoenix WinNonlin (Pharsight Corporation, Princeton, NJ, USA; Version 7.0 or higher) will be used to calculate peak viral load (VL) and the area under the viral load-time curve (VL AUC). Viral load at each study visit, proportion of subjects with negative results at each study visit, peak VL, and VL AUC based on qRT-PCR and TCID₅₀ from nasopharyngeal secretions will be summarized with n, mean, SD, geometric mean, CV, minimum and maximum values in the mITT population overall and per influenza A virus subtype. All available viral data within the mITT population will be assessed to calculate proportion of subjects with negative results at each study visit. For all other calculated parameters, viral load will be assessed on all samples in the mITT population collected through the Day 7 visit. In addition, VL and VL AUC for the first 50 subjects will be listed through Day 14 (no summary statistics will be presented). For missing data on Day 3, Day 5 and Day 7, the analysis will be conducted without imputation and with the last observable measurement carried forward (LOCF). For missing data on Day 1, the analysis will be conducted by replacing the missing data with the Day 3 observable measurement. Subjects missing both Day 1 and Day 3 virology data will be removed from the analysis.

A t-test will be used to assess the difference between treatment groups in the VL AUC and peak VL from nasopharyngeal swabs based on qRT-PCR and TCID₅₀. If the assumptions needed for the t-test are not met, log transformation and/or non-parametric methods will be used.

Chi-square methods will be used to compare differences in treatment groups relative to placebo for the proportion of subjects with negative results on Day 3, Day 5 and Day 7 study visits.

A sensitivity analysis will also be performed; the data summary will be repeated in the mITT population excluding subjects who received antiviral therapy during the study. Determination of applicable antiviral therapy will be defined before the study is unblinded. All viral load data generated per the analytical plan will be listed.

For the influenza A virus subtype H3, virus load data measured by TCID₅₀ will be read out by both hemagglutination and NP-ELISA. The sensitivity is higher for NP-ELISA; therefore, all viral load parameters will be calculated using the data from NP-ELISA only.

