- ¹⁸ Sample collected within 30 minutes after completing the infusion of VIS410/placebo.
- ¹⁹ Nasopharyngeal swabs will be obtained from both nostrils (1 swab per nostril).
- ²⁰ Will be done for the first 50 subjects enrolled only.
- ²¹ If a subject presents with or reports influenza-like illness, additional swabs (1 swab per nostril) should be taken (see Section 7.1.5).

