14.3.5.12	Vital Signs – Shift Tables of Not Done, Normal, Abnormal, and Clinically Significant	Safety
14.3.5.13	Summary of PCS Vital Sign Values	Safety
14.3.5.14	Electrocardiogram – Summary and Change from Baseline of QT Intervals	Safety
14.3.5.15	Electrocardiogram - Summary of Normal and Abnormal Results	Safety
14.3.5.16	Electrocardiogram – Shift Table of Normal and Abnormal Results	Safety
14.3.5.17	Electrocardiogram – Categorical Summary of QTcF Changes	Safety
14.4.1.1	Summary of Serum VIS410 Concentrations	PK
14.4.1.2	Summary of Serum VIS410 Pharmacokinetic Parameters	PK
14.4.1.3	Summary of Nasopharyngeal VIS410 Concentrations	PK
14.4.1.4	Summary of Nasopharyngeal VIS410 Pharmacokinetic Parameters	PK
14.4.2.1	Summary of Anti-influenza A Antibodies	mITT
14.4.2.2	Area Under the Viral Load-Time Curve (VL AUC) and Peak Viral Load (VL) Based on qRT-PCR from Nasopharyngeal Swabs Through Day 7 <Viral Load Parameters Determined by qRT-PCR>	mITT
14.4.2.3	Area Under the Viral Load-Time Curve (VL AUC) and Peak Viral Load (VL) Based on TCID ₅₀ from Nasopharyngeal Swabs Through Day 7 <Viral Load Parameters Determined by TCID ₅₀ >	mITT
14.4.2.4	Kaplan-Meier Estimates of Median Time to Resolution of Viral Load Measured by qRT-PCR Through Day 7	mITT
14.4.2.5	Kaplan-Meier Estimates of Median Time to Resolution of Viral Load Measured by TCID ₅₀ Through Day 7	mITT
14.4.2.6	Percent of Subjects Negative for Viral Titer by Study Day Determined by qRT-PCR	mITT
14.4.2.7	Percent of Subjects Negative for Viral Titer by Study Day Determined by TCID ₅₀	mITT
14.4.2.8	Summary of Anti-VIS410 Antibody Titer	mITT

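### A Day 14 percent-negative figure under SAP 11.2 and 16.1 would measure clearance among subjects still positive on Day 7, so it is not comparable with the Day 3, 5 and 7 rates

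*SAP*

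**What the plan says.** SAP 11.2 handles proportion negative differently from the other viral summaries. For proportion negative, "All available viral data within the mITT population will be assessed to calculate proportion of subjects with negative results at each study visit". In contrast, "For all other calculated parameters, viral load will be assessed on all samples in the mITT population collected through the Day 7 visit". Viral load and VL AUC for the first 50 subjects are listed to Day 14, without summary statistics.

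SAP 16.1 then limits the laboratory work. Viral load samples are assayed to Day 7, "unless still positive on Day 7, and then samples will also be analyzed on Day 14". Beyond that, "No PCR or TCID₅₀ samples are planned to be analyzed post-Day 14".

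Footnote 21 of Protocol Table 1 applies to the swabs from Day 14 onward: "Will be done for the first 50 subjects enrolled only". SAP 16.2 repeats the limit and, like the protocol, adds an exception: "If a subject presents with or reports influenza-like illness, additional swabs (1 swab per nostril) should be taken".

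The planned outputs are Table 14.4.2.6, "Percent of Subjects Negative for Viral Titer by Study Day Determined by qRT-PCR", and its TCID50 counterpart, Table 14.4.2.7. The titles of Tables 14.4.2.2 to 14.4.2.5 all state a Day 7 limit; these two do not.

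Last observation carried forward is specified for Days 3, 5 and 7 only (SAP 11.2), and other missing data are generally left missing (SAP 4.2).

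**The concern.** Taken one at a time, these provisions are unremarkable. Together they select the Day 14 sample on an outcome measured after randomization, and one that treatment is meant to change. A first-50 subject who cleared by Day 7 has a scheduled Day 14 swab that is not assayed, and no rule returns that subject to the Day 14 denominator. A subject still positive on Day 7 is assayed and counted.

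A Day 14 column built this way would stand beside Day 3, 5 and 7 columns that carry no such condition. A reader would naturally follow the row across. The percentage could seem to drop after Day 7 although nobody had relapsed, or the arms could look alike or reversed at Day 14 when their full clearance rates differ. Viral shedding is a secondary objective and emergence of resistant virus is an exploratory one, so a spurious late fall could draw attention.

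**Working it through.** The plan states no Day 14 rate, so there is no figure to reproduce. The check asks what the planned percentage estimates.

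**Inputs from the documents**
- Day 14 assay only if positive on Day 7: SAP 16.1.
- Scheduled Day 14 swabs for the first 50 enrolled: Protocol Table 1 and SAP 16.2.
- 1:1:1 allocation: SAP 2.2. This gives 50/3, about 17 per arm, before any exclusions from mITT.
- No carrying forward to Day 14: SAP 11.2 and 4.2. The zero imputation in SAP 11.2.1 does not help. It covers qPCR-negative samples not tested for TCID50, not samples never assayed by qPCR.

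**Assumed inputs** (the documents give none)
- q, the share negative on Day 7: 0.30 to 0.90.
- c, the share of Day 7 positives who are negative on Day 14: 0.40 to 0.90.
- No Day 7 negative reverts, one assay defines positivity throughout, and there are no influenza-like-illness swabs.

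**Formulas**
- Underlying Day 14 negative rate: U = q + (1 − q)c.
- Rate among assayed samples: c, which does not depend on q.
- Apparent change from Day 7: c − q. True change: (1 − q)c, always positive.
- Expected number assayed per arm: 17(1 − q).

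**Results**

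| Case | Arm | q | c | Shown on Day 14 | Underlying rate U |
|---|---|---|---|---|---|
| Difference masked | Placebo | 0.40 | 0.60 | 60% | 0.40 + 0.60 × 0.60 = 76% |
| | VIS410 | 0.70 | 0.60 | 60% | 0.70 + 0.30 × 0.60 = 88% |
| Order reversed | Placebo | 0.40 | 0.70 | 70% | 0.40 + 0.60 × 0.70 = 82% |
| | VIS410 | 0.75 | 0.50 | 50% | 0.75 + 0.25 × 0.50 = 87.5% |
| Apparent fall | One arm | 0.75 | 0.60 | 75% on Day 7, then 60% | 0.75 + 0.25 × 0.60 = 90% |

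- An apparent fall occurs whenever c < q. Over the assumed range, the shown change runs from 0.40 − 0.90 = −50 points to 0.90 − 0.30 = +60 points. The true change runs from 0.10 × 0.40 = +4 to 0.70 × 0.90 = +63 points.
- With q at 0.40 and 0.70 and the same c in both arms, the row shows no difference. The underlying difference is 0.30(1 − c): 18 points at c = 0.40 and 3 points at c = 0.90.
- Subjects assayed per arm: 17 × 0.70 = 11.9, 17 × 0.30 = 5.1 and 17 × 0.10 = 1.7 for q = 0.30, 0.70 and 0.90. A combined VIS410 column would have about twice as many.

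**Illustrative counts, 17 per arm.** Suppose placebo has 7 negative on Day 7, with 6 of the other 10 clearing, and VIS410 has 12 negative, with 3 of the other 5 clearing.
- Assayed samples only: 6/10 = 60% (exact 95% CI 26% to 88%) against 3/5 = 60% (15% to 95%).
- Day 7 negatives counted as negative: 13/17 = 76.5% against 15/17 = 88.2%.
- Divided by all 17 without crediting Day 7 negatives: 6/17 = 35% against 3/17 = 18%, which is worse.

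**If 10% of Day 7 negatives revert**, the masked case has underlying rates of 0.40 × 0.90 + 0.60 × 0.60 = 72% and 0.70 × 0.90 + 0.30 × 0.60 = 81%. The assayed row still reads 60% in both arms. Carrying Day 7 negatives forward would give 76% and 88%, too high by 4 and 7 points.

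**The case against.** The SAP does not actually specify a Day 14 row or its denominator. It gives only table titles, and the shells are in a separate document. Since the SAP withholds Day 14 summary statistics for viral load and VL AUC, the same may be intended here. That stands as far as it goes, and the point is therefore about any Day 14 percentage that is produced. But SAP 11.2 exempts proportion negative from the Day 7 cut and applies it at each visit, so a programmer following the text would produce the row.

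A reader might infer that the plan could conceal a treatment effect on virology. The documents do not support that. The chi-square comparisons cover Days 3, 5 and 7, and VL AUC, peak viral load and time to resolution stop at the Day 7 visit. Proportion negative is not a listed endpoint. In the masked case above, the 40% against 70% contrast is visible and tested on Day 7.

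It would also be too strong to say that only first-50 subjects can contribute, or that everyone who cleared is missing from both tables. Influenza-like-illness swabs could add a few later enrollees. SAP 16.1 does not name the assay that defines still positive. If it is qPCR, a subject who is qPCR-positive but TCID50-negative on Day 7 is assayed on Day 14. The TCID50 row is then conditional on qPCR positivity, and the formula above does not carry over to Table 14.4.2.7 with q read as TCID50 negativity.

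**Conclusion.** The point holds for the descriptive Day 14 row. Following the stated rules gives an estimate of clearance among Day 7 positives, drawn almost entirely from first-50 mITT subjects, next to earlier rates that carry no such condition. The row can show a fall when clearance has continued, and it can mask or reverse a difference between arms.

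The mechanism follows from the SAP text, but the size does not: every rate used here is assumed. The counts also assume near-equal arms among the first 50 and no loss to the mITT definition. At about 5 to 12 assayed subjects per arm, for q from 0.70 down to 0.30, the row would be imprecise even if correctly labelled. A late fall in it should not be read as rebound, and real reversion after a negative Day 7 result could not be seen from the scheduled samples.

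**What to change.** In SAP 11.2, limit proportion negative to visits through Day 7, and put that limit in the titles of Tables 14.4.2.6 and 14.4.2.7. List Day 14 results separately as clearance among subjects positive on Day 7, with n per arm. Name in SAP 16.1 the assay that defines positivity on Day 7, and flag any result that comes from an influenza-like-illness swab.

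If a Day 14 rate is still wanted, show it only as a supplement in first-50 mITT subjects, with Day 7 negatives counted as negative and the denominator printed. Label it as assuming no reversion; that matters because relapse or reinfection is a secondary endpoint.

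The cost is a sentence in each of two SAP sections, two table titles and a listing or footnote. No extra samples or assays are needed. SAP 16.7 says the shells are completed after the SAP text is final, so the change can go in before they are fixed.
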